2.7. Safety Variables

2.7.1. Adverse Events, Serious Adverse Events, and Other Safety Reporting

Adverse events will be reported by the subject (or when appropriate, by a caregiver, a surrogate, or the subject's legally authorized representative).

The investigator and any qualified designees are responsible for detecting, documenting, and recording events that meet the definition of an Adverse Event (AE) or SAE. The investigator is responsible for following up on all AEs that are serious, considered related to the study drug or study procedures, or that caused the subject to discontinue the study drug.

2.7.1.1. Events of Special Interest

Based on the class effects or potential risks with IL-17 inhibitors, the following events of special interest will be monitored:

- Candida infection
- Inflammatory bowel disease

In addition, based on the potential risk with an IL-17 receptor inhibitor the following event of special interest will also be monitored:

- Suicidal ideation
- Malignancies
- Major cardiovascular and cerebrovascular events
- Tuberculosis
- Infections (including opportunistic infections and serious infections)
- Cytopenias
- Hypersensitivity reactions

2.7.2. Clinical Safety Laboratory Tests

• See SAP

• Table 1 Laboratory *Tests* for the list of clinical laboratory tests to be performed and the SoA in the protocol for the timing and frequency.

2.7.3. Vital Signs

Vital signs will be measured in a sitting position after 5 minutes of rest and will include temperature, systolic and diastolic blood pressure, pulse, (collected as "Heart rate" in the CRF) and respiratory rate.

2.7.4. Physical Examination

A complete physical examination will include, at a minimum, assessments of the dermatological, cardiovascular, respiratory, gastrointestinal, and neurological systems.

Clinically significant findings observed prior to the first dose of study drug should be listed as medical history in the CRF and reported as AEs if observed after the first dose of the study drug.

2.7.5. Suicidal Ideation and Behavior Risk Monitoring

Suicidal ideation and behavior will be assessed during the study by trained study personnel using the Columbia–Suicide Severity Rating Scale (C-SSRS). The visits at which the C-SSRS assessments will be performed are specified in the SoA in the protocol. The C-SSRS defines 5 subtypes of suicidal ideation and behavior in addition to self-injurious behavior with no suicidal intent.

2.7.6. Pharmacokinetics Variable(s)

Blood samples will be collected for measurement of plasma concentrations of izokibep as specified in the SoA in the protocol.

2.8. Immunogenicity

Antibodies to izokibep will be evaluated in serum samples collected from all subjects according to the SoA in the protocol. These samples will be tested by the sponsor or sponsor's designee.

Samples may be further tested for IL-17A binding domain and albumin binding domain (positive vs negative) and/or in a neutralizing antibody assay.

3. Estimands

The ICH¹ E9 (R1) addendum on estimands² and sensitivity analysis in clinical trials to the guideline on statistical principles for clinical trials came into effect on 30 July 2020. This section addresses the construction of estimands for the primary, secondary, and exploratory objectives. Each estimand is defined according to the following five attributes:

- The **treatment** condition of interest, and as appropriate, the alternative condition to which comparison will be made.
- The **population** of subjects targeted by the clinical question.
- The **variable** (or endpoint) to be obtained for each subject that is required to address the clinical question.
- The clinical question of interest in respect of **other intercurrent events** not covered through the precise specifications of treatment, population and variable.
- A **population-level summary** for the variable providing a basis for comparison between treatment conditions.

3.1. Estimand for the Primary Objective

The main estimand is defined through the following five attributes:

3.1.1. Treatment Condition of Interest

The primary treatment condition of interest is izokibep 160 mg QW and izokibep 160 mg Q2W. The reference treatment condition is the combined placebo, administered either QW or Q2W. Izokibep 160 mg QW and izokibep 160 mg Q2W will each be compared to the combined placebo. Subjects will be analyzed according to their randomized treatment regardless of treatment compliance, use of rescue medications except as noted below, or any other protocol deviations.

3.1.2. Population of Subjects Targeted by the Clinical Question

The population of subjects is males and females ≥ 18 years and ≤ 75 years with moderate to severe HS (AN count of ≥ 5) as further defined by the inclusion criteria and exclusion criteria. The population being studied represents a population normally seen in clinical practice. This ensures the activity of izokibep can be evaluated across a distribution of disease severity in the study.

3.1.3. Variable Obtained from Each Subject Required to Address the Clinical Question

For each subject in the study, the variable to address the clinical question is HiSCR75 at Week 16.

3.1.4. Handling of Intercurrent Events to Reflect the Clinical Question of Interest

The treatment policy strategy approach for the estimand will be used in general, so subjects will be included using observed data at Week 16 regardless of treatment compliance, use of rescue medications except as noted below, or any other protocol deviation. Subjects with missing HiSCR75 assessments at Week 16 will be imputed as non-responders (non-response imputation or NRI). A composite strategy will be used for intercurrent events of receiving oral antibiotic therapy that could affect HS: a list of all subjects who received oral antibiotic therapy that results in such imputation will be finalized after review of all oral antibiotic therapy received by any subject and before unblinding of the study, and will include any subject who initiated a new regimen of tetracycline, clindamycin, and possibly other products, and any subject who was on a stable dose of minocycline or doxycycline at randomization but received a higher dose during the study. The endpoint for such subjects will be imputed using NRI.

3.1.5. Population-level Summary for Comparison Between Treatment Conditions

The population level summary is the response rate, or proportion of subjects who meet HiSCR75 at Week 16 and did not use oral antibiotic therapy that could affect HS before Week 16. The null hypothesis of equal response rates will compare each dosing regimen of izokibep to the combined placebo group respectively. A stratified test of response rates will be implemented in the analysis. If a subject was incorrectly classified during the randomization process, the analysis will use the correct classification, not the classification used during randomization. Within each of the four strata, any prior biologic/Janus Kinase (JAK) inhibitor use for HS (Yes/No) and Hurley Stage (II or III), the response rate for each treatment group and corresponding standard error will be calculated. The difference in response rates (risk difference) will be calculated for each stratum. The common risk difference among the four strata and associated standard error will be estimated by combining the observed risk differences using Cochran-Mantel-Haenszel weighting. The estimated risk difference divided by the standard error will be used as the test statistic and a p-value calculated assuming that the test statistic follows a standard normal distribution under the null hypothesis. Analyses at earlier timepoints when data to calculate the HiSCR75 are collected will also be presented using the same methodology.

The treatment effect will be quantified by the response rate difference of HiSCR75 at Week 16 between placebo and each dosing regimen of izokibep at Week 16.

3.2. Estimands for the secondary objectives

The main estimands for each of the secondary objectives are defined through the same five attributes as listed in the beginning of Section 3.

3.2.1. Treatment Condition of Interest

The primary treatment condition of interest is izokibep 160 mg QW and izokibep 160 mg Q2W. The reference treatment condition is the combined placebo, administered either QW or Q2W. Izokibep 160 mg QW and izokibep 160 mg Q2W will each be compared to the combined placebo. Subjects will be analyzed according to their randomized treatment regardless of treatment compliance, use of rescue medications except as noted below, or any other protocol deviations.

3.2.2. Population of Subjects Targeted by the Clinical Question

The population of subjects is all randomized males and females ≥ 18 years and ≤ 75 years with moderate to severe HS (AN count of ≥ 5) as further defined by the inclusion and exclusion criteria. The population being studied represents a population normally seen in clinical practice. This ensures the activity of izokibep can be evaluated across a distribution of disease severity in the study. Additional restrictions for some endpoints are specified in Section 3.2.3 respectively.

3.2.3. Variable Obtained from Each Subject Required to Address the Clinical Question

For each subject in the study, the variables to address the clinical questions are:

- HS flares through Week 16
- Achieve AN count of 0, 1, or 2 at Week 16. The population will be restricted to the subject with baseline Hurley Stage II
- Achieve at least 3 points reduction from baseline in NRS in Patient Global Assessment of Skin Pain at its worst at Week 16. The population will also be restricted to the subject with baseline NRS \geq 4

3.2.4. Handling of Intercurrent Events to Reflect the Clinical Question of Interest

The secondary efficacy variables of the percentage of subjects who experience HS flare and percentage of subjects who achieved AN count of 0, 1, or 2 among participants with baseline Hurley Stage II will be analyzed analogously to the primary efficacy variable, using a treatment policy strategy approach. Subjects will be analyzed as randomized treatment using observed data regardless of treatment compliance, use of rescue medications, or any other protocol deviation, except for receiving an oral antibiotic that could impact HS. Subjects who received an oral antibiotic that could impact HS will be included in the analysis with NRI in line with a composite strategy.

The secondary efficacy variable of the percentage who achieve at least 3 points reduction from baseline in NRS in Patient Global Assessment of Skin Pain at its worst at Week 16 will be analyzed as a binary variable. The treatment policy strategy approach for the estimand will Final, Version 3.0, 03APR2024 Page 19 of

be used in general, whereby subjects will be included using observed data regardless of treatment compliance, use of rescue medications (except prohibited pain medications), or any other protocol deviation. Using prohibited pain medications at Week 16 will be handled by the composite strategy. Subjects using prohibited pain medications within 28 days of Week 16 will be treated as non-responder with NRI.

3.2.5. Population-level Summary for Comparison between Treatment Conditions

- Percentage of subjects that experience \geq 1 HS flare through 16 weeks of treatment
- Percentage of subjects who achieved AN count of 0, 1, or 2 at Week 16 among participants with baseline Hurley Stage II
- Percentage of subjects achieving at least 3 points reduction from baseline in NRS in Patient Global Assessment of Skin Pain at its worst at Week 16 among participants with baseline NRS ≥ 4. Those who receive prohibited pain medications will be imputed as non-responders.

For each of these endpoints, the difference in proportions will be summarized.

3.2.6. Sensitivity Estimators for the Secondary Estimand

No sensitivity estimators are specified.

3.3. Estimands for the exploratory objectives

Analyses of exploratory objectives will be consistent with analogous primary and secondary objectives.

4. Analysis Sets

In accordance with ICH E3 and E9³, the following analysis sets will be used for the analyses.

4.1. All Screened Set

The All Screened Set will include every subject who has signed the informed consent form. The All Screened Set will be used for summaries of disposition and the associated listing.

4.2. Full Analysis Set

Part A

For assessing efficacy in Part A, the full analysis set (FAS) will include all subjects who receive at least one administration of study drug.

Part B

For assessing the primary and secondary efficacy objectives, all subjects randomized in Part B will be included in the analyses as FAS. Intercurrent events (ICEs) such as missed assessments, missed or discontinued treatment, and protocol deviations, will be addressed as described in the definition of the estimands in Section 17. Subjects will be included according to randomized treatment.

4.3. Safety Analysis Set

Part A

The safety analysis set for subjects in Part A will include all subjects who received at least one administration of test.

Part B

For assessing the safety objectives, all subjects randomized who receive at least one administration of test material will be included in the summaries and analyses. The subject will be grouped according to the actual treatment received; if a subject receives both, the subject will be grouped according to the first actual treatment received.

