9.2. Analysis Sets

Analysis sets will be created separately for subjects enrolled in Part A and Part B. Hypotheses will be tested using only data from Part B.

Full Analysis Set

Part A

For assessing efficacy in Part A, the full analysis set (FAS) will include all subjects who receive at least one administration of study drug.

Part B

For assessing the primary and secondary efficacy objectives, all subjects randomized in Part B will be included in the analyses as FAS. Intercurrent events (ICEs) such as missed assessments, missed or discontinued treatment and protocol deviations, will be addressed as described in the definition of the estimands in Section 9.3. Subjects will be included according to randomized treatment.

For assessment of the third secondary endpoint, the proportion of subjects who achieve AN of 0, 1, or 2 at Week 16, only the subset of subjects in the FAS who have Hurley Stage II at baseline will be included in the assessment. This will be called the FAS for reporting purposes.

Safety Analysis Set

Part A

The safety analysis set for subjects in Part A will include all subjects who received at least one administration of test material.

Part B

For assessing the safety objectives, all subjects randomized who receive at least one administration of test material will be included in the summaries and analyses. In the event that a subject receives incorrect study treatment, that subject will be grouped according to treatment received.

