5.2.2. Handling of Missing Safety Data

In general, missing clinical laboratory data, vital signs, and ECG data will not be imputed. Adverse event imputations for missing severity or relationship are given in Section 6.7.2. Unknown or partial medication and AE date imputations are given below and are to be used only for the assessment of prior/concomitant status for medications and treatment-emergent status for AEs.

5.2.3. Handling of Partial and Missing Dates for Date of Birth, Adverse Events, Prior/ Concomitant Medications

Partial and Missing Dates of Birth

Where the Date of Birth is missing the following convention will be used:

Where the day is missing and month and year are available the day will be completed as the 15th. For example, Date of Birth specified as --JAN1980 will be completed as 15JAN1980.

Missing or Partial Adverse Event and Prior/Concomitant Medication Start/Stop Dates

Missing and/or incomplete dates for medications and AEs are imputed in a manner resulting in the earliest onset or the longest duration during the Treatment Period, whilst ensuring that the start date does not occur after the stop date. The stop date will not be imputed if the medication or AE is "Ongoing". Technically, this will be done as follows:

For a missing/incomplete start date/time the earliest date/time of the following will be imputed:

- The later date of: the earliest possible start date/time, and the date/time of the first dose of treatment.
- The latest possible start date/time.
- The latest possible stop date/time.

For a missing/incomplete stop date/time the later date/time of the following will be imputed:

- The earlier date/time of the latest possible stop date/time and the date/time of last dose of treatment.
- The earliest possible stop date/time.
- The earliest possible start date/time.

Here, the earliest possible date/time is defined as:

- The date/time itself if available.
- The date/time of the first day of the month at 00:00hrs, if month and year are available but the day/time is missing.
- The date/time of the first day of the year at 00:00hrs, if year is available but day/time and month are missing.
- 00:00hrs on the day of informed consent, if the date/time is completely missing.

The latest possible date/time is defined as:

- The date/time itself if available.
- The date/time of the last day of the month at 23:59hrs, if month and year are available but the day/time is missing.

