6.7. Safety

For all Safety Tables, data in Part A and Part B will be summarized as follows, unless otherwise specified:

- Part A summarized with all subjects for the entire time (Week 0 to Week 32)
- Part B, for Period 1, will include the first 16 weeks until the first dose of treatment administered in Period 2 at or after Week 16, summarized by the randomized treatment arms and the combined placebo group (Placebo QW/ Placebo Q2W; Izokibep QW; Izokibep Q2W), and includes all subjects who received at least one dose of study treatment. AEs will be included if date of onset is on or after the day of the first dose received in Period 1 and before the date of the first dose received in Period 2. If a subject did not receive any dose of study treatment in Period 2, all AEs with onset on or after the day of first dose received in Period 1 through 4 weeks (28 days) after the last dose received will be included.
- Part B, Period 2, will include data collected on and after the first dose of study treatment administered at Week 16 visit (or after Week 16 visit, if Week 16 visit is missing), summarized by the randomized treatment groups (Placebo Izokibep QW; Placebo Izokibep Q2W; Izokibep QW; Izokibep Q2W), and includes all subjects who took at least one dose of study treatment in Period 2. AEs will be included if date of onset is on or after the day of first dose received in Period 2 through 4 weeks (28 days) after the last dose received.

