6.7.2. Adverse Events

All SAEs will be collected from the signing of the ICF until the 8-week follow-up visit. All AEs will be collected from the first dose of study drug until 4 weeks after the last dose of study drug. All AEs recorded on the CRF will be coded using the latest MedDRA dictionary around the time of Database Lock and classified as either AEs or TEAEs as follows:

- TEAEs for Part A and Period 1 in Part B are either events with start date and time after the start of the Treatment Period and up to 4 weeks after the end of the Treatment Period (for subjects in Part A or those who don't enter Part B Period 2), or events with start date and time prior to the start of the Period 1 whose severity worsens on or after the start of Period 1 and up to 4 weeks after the end of the Treatment Period (for subjects in Part A or those who don't enter Part B Period 2).
- TEAEs for period 2 in Part B are either events with start date and time after the start of administration of Week 16 treatment and up to 4 weeks after the end of the Treatment Period, or events with start date and time prior to the start of administration of Week 16 treatment whose severity worsens on or after the start of administration of Week 16 treatment through 4 weeks after the end of the treatment period. For subjects who receive treatment in period 2, TEAEs with start date after the start of period 2 will be assigned to period 2 only, not to period 1.
- Treatment-Emergent Serious AEs (TESAEs) will be defined as TEAEs which meet the criteria as Serious = "Yes".
- The relationship between a TEAE and treatment is assessed as related or not related. A treatment-related TEAE will be defined as a TEAE considered by the investigator as related to treatment or with unknown/missing relationship to treatment.
- Assessment of AE intensity will be based on CRF AEs form. Severe TEAEs are defined as TEAEs assessed as being "Severe" in intensity and include those events where the intensity is missing.
- TEAEs leading to discontinuation of treatment are defined as TEAEs where "Action Taken with Study Treatment" is indicated as "Drug Withdrawn".
- Injection site reactions (ISRs) will be defined as any adverse event where the preferred term contains the words "injection site".

In addition to the aforementioned AE types, the following TEAEs of special interest will be summarized:

- Candida infection,
- Inflammatory bowel disease,
- Suicidal ideation.
- Malignancies

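### Incomplete AE onset dates are anchored only to the first dose, so some izokibep-time events in placebo switchers are counted in the placebo period; separately, SAP 4.3 and 6.7 disagree on how a misdosed subject is grouped

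*SAP*

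**What the plan says.** **Dates.** SAP 5.2.3 gives the aim: "Missing and/or incomplete dates for medications and AEs are imputed in a manner resulting in the earliest onset or the longest duration". The imputed start is the earliest of three candidates. The first is "The later date of: the earliest possible start date/time, and the date/time of the first dose of treatment"; the other two are the latest possible start and the latest possible stop. If only the day is missing, the earliest possible date is the first of the month. If the month is missing too, it is 1 January. If nothing is recorded, it is the day of consent, which the first-dose bound then raises to Day 1. SAP 5.2.2 limits imputed AE dates to deciding treatment-emergent status.

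**Periods.** SAP 6.7 puts an AE in Period 1 if onset is on or after the first dose and "before the date of the first dose received in Period 2". Period 2 is "summarized by the randomized treatment groups (Placebo Izokibep QW; Placebo Izokibep Q2W; Izokibep QW; Izokibep Q2W"). SAP 6.7.2 defines treatment emergence separately for the two periods. For subjects dosed in Period 2 it adds that "TEAEs with start date after the start of period 2 will be assigned to period 2 only, not to period 1".

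**Grouping.** SAP 4.3 groups the Part B safety set by actual treatment, and "if a subject receives both, the subject will be grouped according to the first actual treatment received". SAP 6.7 has Period 1 "summarized by the randomized treatment arms and the combined placebo group". Protocol 9.2 says: "In the event that a subject receives incorrect study treatment, that subject will be grouped according to treatment received".

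**The concern.** Setting an unknown onset to the earliest date is cautious when a subject has only one treatment: the event is then counted as on treatment. A placebo subject in Part B has two. The boundary between Period 1 and Period 2 is the switch from placebo to izokibep, so the earliest date is the one that credits the event to placebo. This sits badly with the caution elsewhere in SAP 6.7.2, where missing severity is counted as severe and missing relationship as related. It also blurs the split of switchers by phase that Protocol 9.3.5 calls for.

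At stake are two displays: the combined placebo column in Period 1, and the two small Period 2 columns that show what happens when placebo subjects start izokibep.

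The grouping conflict matters because a subject given the wrong vial could appear in different columns of the same report, and the choice might be made after unblinding.

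**Working it through.** The documents state no figure for this point, so there is none to reproduce. The check applies the written rule.

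**Inputs**
- Part B has about 170 subjects randomized 1:1:2:2 (SAP 2.1). Each placebo group is 170 × 1/6 = 28.3 and both together are 170 × 2/6 = 56.7, matching the stated 28-29 per group.
- The first izokibep dose for a switcher is at Week 16, 112 days after Day 1. The last dose is at Week 31 (QW) or Week 30 (Q2W), and AEs are collected for 28 days after it.
- Period 2 window, both ends included: QW 7 × 31 + 28 − 112 + 1 = 134 days; Q2W 7 × 30 + 28 − 112 + 1 = 127 days.
- Assumptions: onset uniform over the window, no stop date early enough to constrain the start, and first-dose dates spread over 365 days from 1 August 2022.

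**Rule as coded**
Imputed start = min[max(earliest possible start, first dose), latest possible start, latest possible stop].

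**Share of a switcher's true Period 2 events moved to Period 1**

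| What is recorded | QW | Q2W |
|---|---|---|
| Month and year | 11.0% | 11.6% |
| Year only | 81.5% | 82.5% |
| Nothing | 100% | 100% |

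Movement from Period 1 to Period 2 is 0% in every row.

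**Hand check of the first row.** Only the switch month is affected. If the switch dose falls on day d of a 30-day month, days d to 30 are truly Period 2, and all are imputed to the 1st. They are misplaced unless d = 1. The average number of misplaced days is the sum of (31 − d) for d = 2 to 30, divided by 30: 435/30 = 14.5. Then 14.5/134 = 10.8% and 14.5/127 = 11.4%, close to the calendar-based values. The year-only figure is below 100% because an event in the calendar year after the switch is imputed to 1 January of that year, already in Period 2. That figure depends on the assumed enrolment calendar.

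**Example.** First dose 10 January 2023, Week 16 dose 2 May 2023. An AE dated May 2023 is imputed to 1 May, in the placebo period. One dated June 2023 is imputed to 1 June, correctly in Period 2.

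**Size per subject.** A subject with no other such event in that period moves the combined placebo column by 1/57 = 1.75 points and one switcher column by 1/28.5 = 3.5 points.

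**Grouping.** Period 1 has 85 × 16 + 85 × 8 = 2,040 planned administrations, of which 680 are placebo. The first-treatment rule leaves an izokibep-exposed subject under placebo in two cases: an izokibep subject wrongly given placebo first (about 113 first doses), or a placebo subject wrongly given izokibep later (680 − 57 = 623 doses). At an assumed error rate of 0.1% per dose this is (113 + 623) × 0.001 = 0.7 subjects. SAP 4.3 and 6.7 themselves give different columns for a single misdose only when it is the first dose: 170 × 0.001 = 0.17 subjects. For a later misdose both keep the subject in the starting arm, while Protocol 9.2 does not say what happens when both treatments are received.

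**The case against.** Several counter-arguments are sound.

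- **Switchers are already split by period.** SAP 4.3 read alone might suggest that every switcher's izokibep events fall under placebo. SAP 6.7, SAP 6.7.2 and Protocol 9.3.5 prevent this in the by-period tables. Whole-study outputs do pool the two phases: the AESI and injection-site-reaction tables, and the liver Kaplan-Meier plots coloured by randomized arm. However, the column label in SAP 6.1 names the switch.
- **Direction.** A reader might infer that both rules favour izokibep. The documents do not support that. The date rule applies to every arm, so undated Period 2 events in the roughly 113 continuing izokibep subjects also move into Period 1 and raise those columns. The first-treatment rule also works both ways: a placebo subject wrongly given izokibep on Day 1 becomes an izokibep subject.
- **Injection-site reactions.** Protocol 2.2.3.3 reports them often with SC izokibep (61.9% and 38.9%) but gives no placebo rate. It therefore cannot show that an undated reaction more likely began on izokibep.
- **Few dates may be incomplete.** Subjects are watched for at least an hour after dosing at Week 16 and again at Week 17 (QW) or Week 18 (Q2W), and treatment-period visits are at most four weeks apart.
- **Visibility.** Listings keep the original dates, and safety carries no p-values.

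These points limit the size and remove the claim of direction. They do not answer the attribution error. For a continuing izokibep subject the move changes only the period. For a switcher it changes the treatment.

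**Conclusion.** The date point holds. For placebo switchers, the rule places a completely missing onset on Day 1 and a month-only onset in the switch month on the 1st, normally in the placebo period. Month-only dates after the switch month are placed correctly. Under the stated assumptions about 11%, 82% and 100% of true Period 2 events are moved when the day, the day and month, or the whole date is missing, and none move the other way. This rests on reading treatment-emergent status as period-specific, which is how SAP 6.7.2 defines it.

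The clear error is that izokibep-time events appear under placebo and are absent from the Placebo-Izokibep columns of Period 2. The absolute effect cannot be computed because the number of incomplete dates is not known. A net bias of the Period 1 comparison towards izokibep is not established.

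The grouping point holds as an inconsistency, not as a bias: SAP 4.3 and Protocol 9.2 use treatment received, while SAP 6.7 uses randomized arms. Few subjects are likely to be affected, about 0.7 at an assumed 0.1% error rate. Both points are worth correcting before unblinding because the edits are small.

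**What to change.** 1. **SAP 5.2.3.** For placebo-randomized subjects dosed in Period 2: when the recorded date parts, including any stop date, allow onset on or after the first Period 2 dose, set onset to that dose and assign the event to Period 2. Because this alone would leave continuing izokibep subjects' undated events in Period 1, add a sensitivity analysis applying the same anchor to all arms, so that the Period 1 comparison is treated evenly.
2. **SAP 4.3 and 6.7.** State the same as-treated rule in both, applied within each period and consistent with Protocol 9.2. Include what happens when a subject receives both treatments within a period.

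The cost is a few SAP sentences, one change to the date derivation and one extra set of AE summaries. The downside is that a few true placebo-period events with incomplete dates will be counted under izokibep.
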